
Control intervention. Participants in the control arm will receive mailed materials about general fruit and vegetable intake intervention based on published NCI guidelines. (<https://cancercontrol.cancer.gov/ocs/>). The control intervention will utilize the same delivery method (i.e. mailed educational materials, live phone call, IVR calls) and follow the same contact schedule as the treatment schedule (See Appendix P and Appendix Q). We intend to compare our tailored cruciferae program with general program on increase of fruit and vegetable intake. We anticipate minimal contamination between intervention and control because BCS will be recruited throughout our catchment area and our intervention will be delivered individually with each BCS.

Personnel Training. [name] will utilize her extensive experience in training others in the delivery of behavioral interventions to train project staff to implement the intervention. A training-of-trainers model that incorporates didactic education, trainee practice, and written and verbal feedback will be used. Training will build knowledge about behavior change promotion, with a specific emphasis on delivering the live phone call with fidelity, utilizing participant booklets to program the IVR messages, and communicating effectively with participants about health. The training will conclude with project staff demonstrating mastery of concepts through mock phone sessions and live phone calls, and accurate programming based on booklet data received. Project staff will be asked to complete a checklist of topics to monitor intervention fidelity.

Aim 2: Conduct a feasibility pilot of our evidence-based dietary behavioral intervention

Study Design. We will use a Hybrid I implementation randomized-controlled design to simultaneously gather outcomes regarding the intervention's feasibility and process data to facilitate wide-spread implementation and dissemination of the intervention into clinical practice if the intervention is effective. A total of 80 patients will be recruited on a rolling basis. Forty will be randomized to intervention and 40 to control.

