Patient: With n=40 for each group, the ANCOVA can achieve 80% power to detect a difference of 0.57 within-group standard deviations (SDs) between groups assuming the correlation of post-intervention and baseline outcome is R²=0.2. Data from the Be-Well study reports a within-group SD of 8.9 μ M for urinary ITCs and 62 g/day for cruciferae intake; thus, we can detect a difference equivalent to 5.1 μ M in urinary ITC and 35.3 g/day of cruciferae intake between groups. The intervention's goal is to increase urinary ITC levels from the baseline of 4.4 μ M to the desirable biological dose of 10 μ M and cruciferae intake from the baseline of 52.7 gram (0.7 serving) to at least 75 gram (a typical serving size) at 6-month follow up. Given the generally lower cruciferae intake observed in other BCS studies (around 0.44-0.45 serving, equivalent to 33-34 gram per day)^{11, 26}, the proposed study will have sufficient power to detect our projected differences.

Physician: We will recruit up to 20 physicians to ensure data saturation⁶¹. Among clinicians involved in cancer treatment, enrollment rates between 46.3%-92% have been reported^{60, 62, 63}, with one study reporting an enrollment rate of 48% among clinicians involved in bladder cancer treatment⁶². Out of the 80 participants enrolled in our intervention, we anticipate 40 to nominate their physicians and expect to receive referrals for 5 additional physicians from enrolled physicians and 5 physicians nominated by our CAB. Given an anticipated enrollment rate of 48%, we anticipate recruitment of 20 physicians.

Randomization

Subjects will be randomized in a 1:1 fashion to the control arm and interventional arm using permuted block randomization. We will employ random block sizes of 4 and 2. Randomization will be carried out by the Department of Biostatistics and Bioinformatics.

Demographics and Baseline Characteristics

Descriptive statistics (as appropriate: n, percent, mean, median, min and max) will be used to summarize demographic and baseline characteristics. The patient characteristics will also be summarized by treatment group. The baseline characteristics between groups will be compared by independent sample t-tests and Fisher's exact tests as appropriate.

Primary Analysis.

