Fruit and vegetables are plants that have lots of minerals, vitamins, and other healthy things that are good for the human body. A fruit develops from the flower of a plant, while the other parts of the plant are known as vegetables. Fruits have seeds, while vegetables can have roots, stems and leaves.

Some common fruits are:

- Apples and pears
- Citrus – oranges, grapefruits, mandarins and limes
- Stone fruit – nectarines, apricots, peaches and plums
- Tropical and exotic – bananas and mangos
- Berries – strawberries, raspberries, blueberries, kiwi, and passionfruit
- Melons – watermelons and honeydew
- Tomatoes and avocados

Some common vegetable types are:

- Leafy green – lettuce and spinach
- Cruciferous – cabbage, cauliflower, Brussels sprouts and broccoli
- Marrow – pumpkin, cucumber, and zucchini
- Root – potato, sweet potato and yam
- Edible plant stem – celery and asparagus
- Allium – onion, garlic, and shallot

POW-R HEALTH: Power to Redefine Your Health 3

14 POW-R HEALTH: Power to Redefine Your Health

How are fruits and vegetables good for you?

Having a healthy diet full of fruits and vegetables is very important. Research has shown that eating fruits and vegetables can help you live longer. Eating fruits and vegetables reduces the risk of getting some cancers, high blood pressure (hypertension), heart disease, and diabetes. A recent study said that eating about 2 cups (200 g) of fruits and vegetables each day can reduce the risk of heart disease by up to 16%, stroke by 18%, and cancer by 4%. Cancer survivors who eat at least 5 servings of fruits and vegetables report better overall well-being.

Fruits and vegetables have all of these great health benefits because they have a lot of vitamins C and A, electrolytes, and antioxidants. Vitamin C protects the immune system and protects the body from harmful effects of pollutants and toxins. Vitamin C protects cells and molecules from damage that causes many diseases, including cancer. Fruits and vegetables are also a great source of fiber. The fiber in fruits and vegetables lowers cholesterol, which reduces heart disease risk. The fiber in fruits and vegetables can also help control the body's blood sugar, which reduces risk of diabetes. Fruits and vegetables can also help you have a healthy weight by giving you lots of fiber and water, which can fill you up without giving too many calories.

How can you get the best health benefits from eating fruits and vegetables?

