If NO: It's really important that you have your packet before we go over it. Let me make a note to send you the packet again. What is your mailing address? I'll call you again after your packet is sent. Thank you for taking the time to talk with me. I'll talk to you again soon.

END CALL.

A2. If so, did you have time to review the information in this packet?

No	Yes
Mailing Address	
No	Yes

PART B: OVERVIEW

How can you get the best health benefits from fruits and vegetables?

- Vegetables: Fresh, frozen, and canned vegetables can all be a part of healthy eating.
 - Fresh vegetables are best
 - Canned vegetables can be high in salt, so if you buy canned vegetables make sure you look for the 'no salt' ones.
- Fruit: Fresh, frozen, and canned fruit can all be a part of healthy eating
 - Fresh fruit is best
 - Canned fruit can be high in sugar and calories, so buy canned fruit in 100% fruit juice with no sugar added.
 - Be careful of fruit juices! They're high in sugar and calories, and you can miss out on a lot of other vitamins and minerals that eating fruits will give you.
- Eat 2½ to 3 cups of vegetables and 1½ to 2 cups of fruit each day; or a total of 4-5 cups of both fruits and vegetables a day. 1/2 cup is about the size of the **front** of a closed fist. 1 cup is about the size of your entire fist or a baseball.

How to prepare fruits and vegetables?

- You can eat a lot of fruits and vegetables raw. You can also cook them in many different ways too

Tips to Eat More Fruits and Vegetables

- Tips on how to eat more fruits and vegetables are on pages 6-7 of your POW-R Health Magazine.

I'm going to begin by going over the POW-R Magazine. After I go over the magazine's contents, we'll complete your personal action plan. I'll then go over the POW-R Books and the magnet. So let's start with the POW-R Magazine. Please have your POW-R Magazine next to you so you can follow along what I'm going to review.

PART C: MAGAZINE CONTENT

Welcome to the POW-R Health Program (page 2)

- Living a healthy lifestyle is important for bladder cancer survivors
- Eating fruits and vegetables is an important part of health
- Doctors made the **POW-R Health Program** to make sure you live the longest, healthiest life possible

Interesting convo points

What are fruits and vegetables?

- Fruit and vegetables are plants that have lots of minerals, vitamins, and other healthy things that are good for the human body.

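### The sufficient-power statement sets a between-arm detectable difference against a one-arm before-after goal, so it holds only if the control arm changes little, a condition the plan does not state

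*Combined protocol and SAP*

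**What the plan says.** Section 19, Sample Size Determination, takes 40 participants per arm and a baseline-to-follow-up R² of 0.2. On that footing it puts the effect detectable by ANCOVA at 80% power at "a difference of 0.57 within-group standard deviations (SDs) between groups". Using SDs of 8.9 µM and 62 g/day from the Be-Well cohort, it converts this to 5.1 µM of urinary ITC and 35.3 g/day of cruciferous intake, both between groups.

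It then turns to what the programme should achieve. The intervention's "goal is to increase urinary ITC levels from the baseline of" 4.4 µM to 10 µM, and to raise intake from 52.7 g to at least 75 g per day. It notes a lower intake of 33–34 g/day in other bladder cancer survivor studies and concludes that "the proposed study will have sufficient power to detect our projected differences". It gives no separate figure for those differences and no expected control-arm change.

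The Primary Analysis in the same section is an ANCOVA of the between-group difference in change. On the comparator, Section 11 (Control intervention) says: "We intend to compare our tailored cruciferae program with general program on increase of fruit and vegetable intake". Control participants get the same mail-and-phone delivery on the same contact timetable. The control call script in Appendix Q tells them: "Eat 2½ to 3 cups of vegetables" daily. The control magazine in Appendix P lists cruciferous vegetables as one common type ("cabbage, cauliflower, Brussels sprouts and broccoli").

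**The concern.** A detectable difference between arms must be judged against an expected difference between arms, which is the intervention change minus the control change. Section 19 offers only the first term. The intervention goal can stand in for the between-arm difference only if the control change is close to zero.

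That is not self-evident here, because the control arm is active: same contacts, its own daily vegetable target, and cruciferous vegetables among the types named. Section 11 expects little contamination between arms, but its reasons (dispersed recruitment, individual delivery) concern leakage from one participant to another. They do not address how controls respond to their own programme.

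At stake is how a null primary result is read. If controls improve modestly, power for the contrast the trial was set up to make is below the stated level, and a null could be taken as failure of the tailored programme.

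**Working it through.** **Inputs (all Section 19).** 40 per arm, two-sided α = 0.05, R² = 0.2, SD 8.9 µM (ITC) and 62 g/day (intake). Goals: 4.4 → 10 µM; 52.7 → 75 g/day; alternative baseline 33–34 g/day.

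**Formula.** The ANCOVA standard error of the arm difference is SD × √((1 − R²) × 2/n). Here √(0.8 × 2/40) = √0.04 = 0.2, so SE = 0.2 SD: 1.78 µM and 12.4 g/day. Power comes from the noncentral t with 80 − 3 = 77 df and noncentrality (difference ÷ SE).

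**Reproducing the plan.** At 0.57 SD the noncentrality is 0.57/0.2 = 2.85 and power is 80.4%. The exact 80% point is 0.567 SD. Then 0.57 × 8.9 = 5.07 µM and 0.57 × 62 = 35.3 g/day. The plan's figures are right.

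**Putting the control change in.** Between-arm difference = goal change − control change. The documents give no control change, so the values in the first column are assumptions.

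ITC, goal change 10 − 4.4 = 5.6 µM:

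| Control rise (µM) | Difference (µM) | Power |
|---|---|---|
| 0 | 5.6 | 87% |
| 0.5 | 5.1 | 81% |
| 1.0 | 4.6 | 72% |
| 1.5 | 4.1 | 62% |
| 2.0 | 3.6 | 52% |

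Intake, goal 75 g/day:

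| Control rise (g/day) | From 33–34 g: difference | Power | From 52.7 g: difference | Power |
|---|---|---|---|---|
| 0 | 41–42 | 90–92% | 22.3 | 43% |
| 5 | 36–37 | 82–84% | 17.3 | 28% |
| 10 | 31–32 | 70–72% | 12.3 | 16% |

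**Margin before power drops below 80%.**
- ITC: 5.6 − 0.567 × 8.9 = 5.6 − 5.05 ≈ 0.55 µM, or 0.5 µM against the plan's rounded 5.1.
- Intake from 33–34 g: 0.567 × 62 ≈ 35.2, so 41 − 35.2 = 5.8 to 42 − 35.2 = 6.8 g/day. This is under a tenth of a 75 g serving.
- Intake from 52.7 g: 22.3 − 35.2 = −12.9 g/day. There is no margin; the goal is smaller than the detectable difference before any control change is considered.

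**The case against.** The best defence is in Section 2. An earlier trial in bladder cancer survivors raised vegetable intake from 2.4 to 3.9 servings a day without raising cruciferous intake, and ITC levels at six months were similar in its two arms. If vegetable advice leaves these outcomes unchanged, a near-flat control is a reasonable expectation. The control materials point the same way. No control recipe in Appendix P has a cruciferous vegetable as its main ingredient, boiling, stewing and canned vegetables are allowed, and there is no advice on timing. Section 2 says ITC yield differs up to 300-fold between raw vegetables and falls with heavy cooking, so extra grams in controls need not become extra urinary ITC. This stands as support for a small control change. It does not rescue the statement as written: Section 19 does not invoke it, Section 2 describes a pilot of 48 survivors, and finding no increase in a trial of that size does not exclude a rise of 6–7 g/day.

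The intake goal is also a floor. A mean above 75 g widens the margin gram for gram, although from 52.7 g the intervention mean would have to reach 52.7 + 35.3 = 88.0 g/day for 80% power even with a flat control. Section 19 will also report each arm's change with confidence intervals, so a control rise would be visible. That limits misreading afterwards; it does not make the prospective claim correct.

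Three stronger readings are tempting and not supported:
- That the power arithmetic is wrong. It reproduces.
- That the claim requires exactly zero control change. It tolerates about 0.5 µM, or 6–7 g/day from the lower baseline.
- That controls might gain about 20 g/day, from applying a cruciferous share of 0.44/2.4 to the earlier trial's 1.5-serving gain (0.44/2.4 × 1.5 × 75 = 20.6). Section 2 says that very gain came without an increase in cruciferous intake, so the trial cannot supply this bound.

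**Conclusion.** The concern holds as a missing condition on the power claim, not as a calculation error. For ITC, 80% power is available only if the control arm rises by no more than about 0.5 µM. For intake, the limit is about 6–7 g/day if baseline is 33–34 g; for the stated 52.7 to 75 g goal, power is about 43% with a flat control, so the claim fails there whatever the control arm does.

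These figures assume all 40 participants per arm contribute outcomes, R² = 0.2, and Be-Well SDs that stay the same at follow-up, including for ITC when the intervention mean more than doubles. A reader should not infer that the trial is underpowered for ITC. The documents do not give the control change, and what evidence they cite favours a small one.

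**What to change.** Rewrite the closing sentences of Sample Size Determination in Section 19:

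1. Define the projected difference as intervention change minus control change at six months, for each primary outcome.
2. State the control change assumed. The earlier survivor trial in Section 2 may be cited as support for a small one, noting that it is a single small pilot.
3. Replace the sufficient-power sentence with a conditional one: with 40 per arm, 80% power holds for a control rise of up to about 0.5 µM in ITC, or up to about 6–7 g/day in intake if baseline is 33–34 g/day, and is not reached for a change from 52.7 to 75 g/day.
4. Give power at a few control changes, labelled as assumptions (for example 0, 0.5, 1 and 2 µM; 0, 5 and 10 g/day), and name the baseline for each intake figure.

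The sample size stays at 80, and neither the analysis nor the conduct of the trial changes. The cost is a rewritten paragraph and a less favourable power statement.

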20. PROVISIONS TO MONITOR THE DATA TO ENSURE THE SAFETY OF SUBJECTS

N/A

21. VULNERABLE POPULATIONS

N/A

22. COMMUNITY-BASED PARTICIPATORY RESEARCH

The study does not use a “pure” community-based participatory research approach but does include community engagement, which will include engagement of a Community Advisory Board to develop the cruciferae intervention.

23. SHARING OF RESULTS WITH SUBJECTS

Aggregate study results will be disseminated to the project's Community Advisory Board, the Bladder Cancer Survivorship Group at Roswell Park Comprehensive Cancer Center, the New York State Department of Health Cancer Registry, and to participating patients and health care providers who consented to be part of the research, written informed consent for participating patients and verbal consent for participating health care providers. Study participants will be mailed aggregate study results with no personal identifiers. Study results will also be disseminated to academic and practice audiences through scientific papers and conferences.

24. SETTING

Participant Recruitment. NYSCR will send a letter to the physician of record for selected cases notifying him/her that the patient was identified for the study, requesting that NYSCR be notified if the patient is unable or ineligible to participate in the study, and requesting information about the case's primary care physician if different from the contacted physician. If no contraindication has been received from the physician or if the physician has not responded within 3 weeks, the NYSCR will send an informational packet to the patient. The packet will contain: 1) a letter with study information; 2) a participant information sheet; and 3) a release of information consent form. After two weeks without response, a reminder packet will be sent and followed with up to five phone calls. If NYSCR can't reach the patient, the patient will be considered a refusal. The NYSCR's materials and procedures will be reviewed by the New York State Department of Health IRB. For patients who agree to be contacted about the study, the NYSCR will securely share the patient's name, contact information, and information about their diagnosis with the Roswell study team. For the Roswell Park Cancer Registry: study staff will consult with Roswell Park urologist

to determine if the patient is unable or ineligible to participate in the study. The patients accessioned from the Roswell Park Cancer Registry will be contacted by letter (See Appendix T) asking them to participate in the study. Study staff will follow-up with potential participants to determine whether they received the letter and if they are interested in participating. We estimate that from the pool of at least 100 patients who consent to be contacted, we will be able to obtain informed consent from at least 80 patients (80%). Research staff will contact patients who have agreed to be contacted by phone, whereby they will provide a general study overview and conduct a screening interview to confirm eligibility. The consent form will be mailed out to patients prior to the consenting discussion. We will ask the patient to mail back the consent form with the appropriate signatures. We will also provide an additional copy of the consent form for their records. We will include a paid postage pre-addressed envelope for the patient to mail back the signed consent form to study staff. To assist with study retention, we will ask participants for contact information to be used in follow-up. The Roswell study team will share information with the NYSCR team on the patients who agree to participate in the study, as well as any information obtained from study participants that does not match the information provided from the NYSCR database (e.g., race, ethnicity).

The process for contacting the patient, including the number of contact attempts, the letter text and/or phone script, the consent form, the data to be collected, and information on any incentives for participation will be reviewed by the NYSCR, New York State Department of Health (NYSDOH), and the NYSDOH IRB prior to the initiation of any patient/proxy contact. In addition, the research team will follow all NYSDOH procedures in conducting their study, including the following procedures:

1. All written materials must include contact information for people who can answer questions about the research and participant rights.
2. Patient consent to participate must be obtained.
3. If a patient asks to be removed from current or future research studies, this information must be sent within two weeks to the NYSCR, so that the patient's record can be flagged and the patient added to a "Do Not Contact" list.
4. Researchers must immediately report any complaints about the study or the release of patient information to the Director of the NYSCR and to the Administrator of the NYSDOH IRB.

If changes are made to any recruitment materials or processes after NYSDOH departmental and IRB approval, an IRB amendment must be submitted and approved before the changed materials may be used.

Before receiving case-level Registry data, the Principal Investigator for a research study will be required to read and sign a Research Data Use Agreement. This contract describes limitations on the use of the data, as well as restrictions on the dissemination of findings, use of personal identifiers, and contact with patients identified through data provided by the NYSCR. All staff working with confidential data, or with possible access to confidential information from the data, are required to have current IRB training certification and to sign a Confidentiality Pledge. The Research Data Use Agreement and Confidentiality Pledge documents can be obtained by emailing the NYSCR at [contact].

Researchers must agree to maintain the confidentiality of identifiable data received from the NYSCR. Identifiable data include any information that would permit, directly or indirectly, the identification of any individual. When applying to use the data, researchers should indicate how the data will be stored as well as how and when they will dispose of the data after the study is completed. In addition, researchers must attest that: 1) no data will be published or released in any form where a particular individual or establishment is directly or indirectly identifiable; 2) identifiable data obtained from the NYSCR will be used only for the proposed study; 3) identifiable information obtained from the NYSCR will not be released to anyone or any institution without prior written approval by the NYSDOH; and 4) any publication or report produced using the data will acknowledge the source of the data. In the event of a breach of confidentiality, researchers must notify the Director of the NYSCR as soon as possible but no later than two business days after learning of the breach.

Physician Recruitment. Research staff will mail an invitation letter to nominated physicians that will include an information sheet (Appendix J), opt-in/opt-card card, and stamped reply envelope. Within 2-weeks, physicians who do not respond will be contacted by phone, fax, or email with no more than 5 attempts. Participating physicians will receive \$100. Physicians who verbally consent to participate will be asked to refer other physicians to the study. CAB members will also utilize their networks to nominate physicians for staff to contact.

